## **6 STATISTICS**

### **6.1 DESCRIPTION OF STATISTICAL METHODS**

The primary analysis of the trial will be an intention-to-treat analysis comparing intervention (HRMP) against control (SCS) for all primary and secondary outcomes. The primary endpoint, one year graft survival, will be analysed using logistic regression with adjustment for stratification factors. Additional analyses adjusting for other important prognostic factors will also be undertaken. Binary outcomes will be assessed using chi-squared tests and logistic regression to adjust for prognostic factors. Continuous outcomes will be compared using the T-test if normally distributed, otherwise using the Mann-Whitney U test. Time-to-event outcomes will be analysed using survival analysis methods, including Kaplan-Meier plots and Cox proportional hazards regression model with calculation of hazard ratios. Outcomes will be reported with 95% confidence intervals and two-sided p-values to 3 decimal places.

A secondary analysis of the primary endpoint will be done as per protocol.

A Statistical Analysis Plan (SAP) containing a detailed description of the statistical methods will be drafted as a separate document early in the trial and finalised prior to the final data lock.

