#### **4.4.4 Randomisation**

##### **4.4.4.1 Allocation: Sequence generation**

Recruiting site personnel will be responsible for randomisation of individual kidneys. Kidneys will be randomly assigned to either cold storage or machine perfusion group with a 1:1 allocation as per a computer generated randomisation schedule held centrally by the trial office. The allocation will be stratified by centre.

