## **6.2 NUMBER OF PARTICIPANTS**

### Sample size calculation

Based on the previously published paper by Treckmann et al., the 1-year graft survival for ECD kidneys preserved by SCS is being estimated at 80%. The use of HRMP is being hypothesized to improve 1-year graft survival from 80% to 92% based upon the improvement in graft survival of ECD kidneys seen in the MP Trial.

For a power of 80% with Type I error (alpha) of 5%, in a two-sided statistical model, the required sample size to detect an improvement in 1-year graft survival from 80% to 92% is 131 kidneys in each treatment arm, 262 in total.

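### The primary model adjusts for centre only, although baseline prognostic values are recorded before allocation is revealed: a modest missed gain in power, not an error

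*Protocol*

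**What the plan says.** Section 6.1 fixes the primary model: "The primary endpoint, one year graft survival, will be analysed using logistic regression with adjustment for stratification factors". Section 4.4.4.1 gives the one stratification factor: "The allocation will be stratified by centre". Section 6.1 then puts any further adjustment outside the primary analysis: "Additional analyses adjusting for other important prognostic factors will also be undertaken". Those factors are not named.

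Section 4.4.4.2 withholds the allocation until the recipient has been recruited and the donor and recipient baseline characteristics have been entered. Donor age and terminal creatinine are among the donor eligibility criteria (4.3.2), and both first and repeat transplants are admitted (4.3.3).

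The sample size in section 6.2 compares 1-year graft survival of 80% with 92%: "For a power of 80% with Type I error (alpha) of 5%, in a two-sided statistical model", giving "131 kidneys in each treatment arm, 262 in total". Section 6.1 promises confidence intervals and p-values but names no effect measure for the primary endpoint. It leaves detailed methods to the SAP.

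**The concern.** The protocol accepts that important prognostic factors other than centre exist, and its Background says that kidneys from older and more marginal donors have poorer long-term graft survival. Yet the model for the primary result ignores them. In logistic regression, adjusting for a baseline variable that predicts the outcome raises the power of the treatment test. Here the planned power is close to the 80% target and few graft losses are expected, so precision is scarce and the data needed to improve it are already being collected.

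A lesser matter is reporting. Logistic regression yields an odds ratio by default, while the benefit was planned as 12 percentage points of graft survival. The odds ratio alone would not tell a reader whether a gain of that size was reached.

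**Working it through.** **Inputs from the protocol.** Survival 80% and 92%, two-sided alpha 5%, power 80%, 131 per arm (6.2); 1:1 allocation (4.1); stratification by centre (4.4.4.1); four named centres (6.3). The prognostic strength of the covariates is not given, so a range is assumed.

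**1. The planned sample size.** Pooled-variance formula, no continuity correction:

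n = [z(0.975)·√(2·p̄·(1−p̄)) + z(0.80)·√(p1(1−p1) + p2(1−p2))]² / (p2−p1)², with p̄ = 0.86

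= [1.960·√0.2408 + 0.842·√0.2336]² / 0.12² = (0.962 + 0.407)² / 0.0144 ≈ 130.1, rounded up to 131 per arm.

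This matches the protocol. Power at 131 per arm is 80.3%.

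**2. Expected losses.** 131 × 0.20 + 131 × 0.08 = 26.2 + 10.5 ≈ 37. A model with arm, three centre terms and three covariates has 7 coefficients besides the intercept: 36.7 / 7 ≈ 5.2 losses per coefficient. If two centres were added (an illustration; 6.3 allows additional centres), it would be 36.7 / 9 ≈ 4.1.

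**3. Power with and without a prognostic score.** Simulation of 262 kidneys, 4,000 trials per scenario. Four centres of assumed size 72/68/68/54, balanced allocation within centre, and marginal survival held at 80% and 92%. One standard normal baseline score stands for all covariates. Wald test:

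| Log-odds slope per SD (assumed) | AUC of score | Centre only | Centre + score | Gain (points) |
|---|---|---|---|---|
| 0 | 0.50 | 81.5% | 81.3% | −0.2 |
| 0.4 | 0.61 | 82.5% | 83.0% | 0.5 |
| 0.6 | 0.66 | 81.5% | 82.8% | 1.3 |
| 0.8 | 0.71 | 81.3% | 83.8% | 2.5 |
| 1.0 | 0.74 | 82.0% | 86.4% | 4.4 |
| 1.3 | 0.79 | 81.2% | 87.3% | 6.1 |

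Likelihood-ratio gains are similar: 0.3 to 5.7 points for AUC 0.61 to 0.79. Type I error at AUC 0.71 is 4.3% with either model. Monte Carlo error is about ±1.2 points on each power figure.

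**4. Other simulation set-ups.**
- Centres of 78/73/72/39 with between-centre variation (SD 0.3 on the logit scale), likelihood-ratio test, slopes 0.4, 0.6, 0.8 and 1.0: 82.6 to 83.1%, 82.6 to 84.3%, 82.0 to 85.1%, and 83.2 to 86.4%. The gains are 0.5, 1.7, 3.1 and 3.2 points.
- Donor age, creatinine and repeat transplant entered as three separate terms (15% repeat transplants assumed), likelihood-ratio test: uninformative 82.7 to 82.1%; weak 81.3 to 82.6%; moderate 82.4 to 84.0%; stronger 81.5 to 84.7%. Type I error was 5.2 to 5.9% adjusted, against 5.0 to 5.5% with centre only.

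**5. Scale of the effect.** The planned rates correspond to an odds ratio for survival of (0.92/0.08) / (0.80/0.20) = 11.5 / 4 = 2.875. For loss it is 1/2.875 = 0.348, where the risk ratio is 0.08/0.20 = 0.40. Holding 2.875 fixed and varying control survival:

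| Control survival | Survival with HRMP | Difference (points) |
|---|---|---|
| 75% | 89.6% | 14.6 |
| 80% | 92.0% | 12.0 |
| 85% | 94.2% | 9.2 |
| 90% | 96.3% | 6.3 |

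**The case against.** The strongest defence is that the plan is coherent. The primary model matches the randomisation, prognostic adjustment is already promised, and the choice of covariates and summary measure is ordinary SAP content. The centre-only model meets its stated power, and nothing in the protocol shows how well donor age, creatinine or repeat transplantation predict graft loss in a population whose donor age is already restricted by eligibility. Seven coefficients on about 37 losses is also not generous.

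Most of this stands, and it limits the point to a missed efficiency. It does not remove the point, because 6.1 itself fixes what the primary model contains. A SAP that follows 6.1 can name the factors for the additional analyses but cannot move them into the primary one.

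Three stronger readings are tempting and are not supported:
- **That the odds ratio conflicts with the sample size.** Survival of 80% against 92% is both a 12-point difference and an odds ratio of 2.875, so the planning comparison and the logistic model share the same null and the same alternative. Section 6.1 names no effect measure, and the difference can be obtained from the same model.
- **That the trial is too small for a logistic analysis.** A large-sample Wald formula on the log odds ratio gives 139.6 per arm, but simulating the planned analysis at 131 per arm gives power above 80%.
- **That adjustment is free and the covariates are known to be strong.** It has small costs, and the strength is an assumption.

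**Conclusion.** The point holds as a modest missed efficiency. The planned analysis is valid, its sample size reproduces, and centre-only adjustment keeps about 81 to 83% simulated power under the planned rates. Adding a few baseline covariates would gain about 0 to 3 points if they are weakly to moderately prognostic. The gain is about 4 to 6 points if they are strongly prognostic (AUC about 0.74 to 0.79), although one set-up gave only about 3 points at a slope of 1.0. Type I error stays near 5%. If the covariates carry no information, the loss was 0.2 to 0.6 points, within simulation error.

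These figures rest on assumed covariate strengths, assumed centre sizes, four centres, and the planned survival rates. The standardised survival difference is a useful addition to the reporting; its absence from 6.1 is not a fault.

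**What to change.** Before data lock, and without sight of outcomes by arm, amend section 6.1 and align the SAP:

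- **Primary model:** logistic regression of 12-month graft survival on arm, centre and donor age (continuous), with at most donor terminal creatinine (continuous) and first versus repeat transplant added.
- **Sensitivity analysis:** the centre-only model now in 6.1.
- **Limits on the list:** go no further than these three covariates, given about 5 losses per coefficient with four centres and fewer if centres are added. Leave out total cold ischaemia time, which is completed only after allocation.
- **Reporting:** from the same model, give the standardised 12-month graft-survival difference with 95% CI beside the odds ratio.

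No new data are needed. The cost is a written amendment with the approvals that section 9.3 requires, an odds ratio that becomes conditional on the chosen covariates, and a negligible loss of power if they prove uninformative.

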#### **4.4.3 Baseline Assessments**

The paper version of the EuroQol EQ-5D-5L questionnaire will be completed at the time of consenting the patient to the trial (Appendix D). Here, index-based values are recorded, in order to facilitate calculation of quality-adjusted life years or months of patient survival, that are used to make a health-economic evaluation. The questionnaire will be completed again at 3 and 12 months. Patients who are not willing to complete this questionnaire, will not be excluded from the study.

Donor and recipient demographics will be recorded as per CRF form.

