## **6.8 HEALTH ECONOMICS ANALYSIS**

An economic analysis will be performed, with the objective of estimating average costs and effectiveness in each arm of the study. This will inform a cost-effectiveness analysis using a health service perspective and incremental cost effectiveness ratios (ICER's) will be reported. Quality adjusted survival will be obtained by administration of the EuroQol EQ-5D-5L questionnaire. Quality of life data will be collected at baseline (at time of consent) and at two study follow-up visit following kidney transplantation (at 3 and 12 months).

Costs will be estimated based upon measured resource use and national unit costs; overall, average and incremental costs will be reported in Euro using purchasing power parity methods to adjust for variation in cost of living across different countries. Resources will include machine and disposables costs, immunosuppression and other drugs, inpatient hospital stays (including intensive care days), and dialysis. Data will be assessed at each follow-up visit as outlined in the CRF.

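### Continuous secondary outcomes are fixed to unadjusted tests, which are valid but give up precision available from centre and baseline EQ-5D-5L

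*Protocol*

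**What the plan says.** Protocol section 6.1 sets the method by type of outcome.

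- Primary endpoint: "The primary endpoint, one year graft survival, will be analysed using logistic regression with adjustment for stratification factors".
- Binary outcomes: "Binary outcomes will be assessed using chi-squared tests and logistic regression to adjust for prognostic factors".
- Continuous outcomes: "Continuous outcomes will be compared using the T-test if normally distributed, otherwise using the Mann-Whitney U test".

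After the primary-endpoint sentence comes a general one: "Additional analyses adjusting for other important prognostic factors will also be undertaken". It names no outcome and no covariate.

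The continuous secondary outcomes in section 4.2.2 are eGFR at day 7 and months 3, 6 and 12, EQ-5D-5L, length of hospital stay and length of dialysis.

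Two pieces of design information are relevant. On randomisation, section 4.4.4.1 says: "The allocation will be stratified by centre". On quality of life, section 4.4.3 says: "The paper version of the EuroQol EQ-5D-5L questionnaire will be completed at the time of consenting the patient to the trial"; the questionnaire is repeated at 3 and 12 months. Section 4.4.3 also lets patients decline it and stay in the study.

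**The concern.** Within one paragraph, the primary endpoint is adjusted for the stratification factor and binary outcomes have an adjusted model. Continuous outcomes have two-sample tests that take no covariate.

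Two kinds of precision are lost. First, blocking within centre balances the arms on centre, so differences between centres largely drop out of the difference in arm means. A plain t-test still counts those differences as noise, so its standard error is too large. Second, a pre-allocation EQ-5D-5L score is normally correlated with later scores, and leaving it out keeps explainable variance in the comparison.

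The rule for choosing the test adds a problem of interpretation. Whether a difference in means or a rank comparison is reported depends on the observed distribution, and the answer can change between time points of the same outcome.

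At stake are the width and readability of secondary results, not the main conclusion of the trial.

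**Working it through.** **The plan's own figure.** Section 6.2 gives 131 per arm for 80% versus 92%, two-sided 5%, power 80%. With pooled variance and no continuity correction:

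n = [1.960·√(2·0.86·0.14) + 0.842·√(0.80·0.20 + 0.92·0.08)]² / 0.12² = (0.962 + 0.407)² / 0.0144 ≈ 130.1, rounded up to 131.

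The stated size reproduces and does not depend on how continuous outcomes are analysed.

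**Inputs for the continuous outcomes.** The protocol gives no standard deviation, no baseline correlation and no centre effect. The ranges below are assumptions. All figures use 131 per arm with complete data.

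**Centre.** Let centre explain a share c of the total variance. Under allocation blocked within centre, the true standard error is about √(1−c) times the one that the t-test uses. So:

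type I error ≈ 2·[1 − Φ(1.960/√(1−c))]

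| c (assumed) | 1.960/√(1−c) | Type I error of t-test |
|---|---|---|
| 0.02 | 1.980 | 4.8% |
| 0.05 | 2.011 | 4.4% |
| 0.10 | 2.066 | 3.9% |

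A simulation checked this: four centres in proportion to the recruitment estimates of section 6.3, total 263 after rounding, permuted blocks of 4 (assumed), 4,000 runs per setting. The Monte Carlo standard error is about 0.3 points near 5%. The first figure in each pair below is for a baseline correlation of 0.4 and the second for 0.6.

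| c | t-test, null | centre-adjusted, null | Power, t-test to centre-adjusted |
|---|---|---|---|
| 0.02 | 4.9%, 5.2% | 5.0%, 5.5% | 79.5 to 80.2; 80.2 to 80.9 |
| 0.05 | 4.7%, 4.2% | 5.1%, 4.7% | 80.0 to 81.3; 80.3 to 81.9 |
| 0.10 | 3.8%, 4.1% | 5.1%, 5.4% | 80.9 to 83.6; 80.3 to 83.2 |

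Centre alone is worth about 1-3 points of power.

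**Baseline EQ-5D-5L.** With correlation r between baseline and follow-up, the residual variance is multiplied by 1−r², the interval width by √(1−r²), and the equivalent unadjusted size is 131/(1−r²). The unadjusted t-test has 80% power for (1.960 + 0.842)·√(2/131) = 0.346 SD. Power for that same difference after adjustment is Φ(2.802/√(1−r²) − 1.960).

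| r (assumed) | 1−r² | Interval narrower by | Equivalent n per arm | Power |
|---|---|---|---|---|
| 0.2 | 0.96 | 2% | 136 | 81.6% |
| 0.3 | 0.91 | 5% | 144 | 83.6% |
| 0.4 | 0.84 | 8% | 156 | 86.4% |
| 0.5 | 0.75 | 13% | 175 | 89.9% |
| 0.6 | 0.64 | 20% | 205 | 93.8% |

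This applies to EQ-5D-5L only. For eGFR, hospital stay and dialysis length the protocol provides no comparable pre-transplant value, so only the centre gain remains.

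**Choosing the test by normality.** In 6,000 simulated null trials for each distribution (normal, two gamma, one lognormal; 131 per arm), a Shapiro-Wilk test decided between t-test and Mann-Whitney. The type I error of the whole procedure was 4.8-5.6%. The highest value came with normal data, where the t-test alone gave 5.5% in the same runs. There is no material inflation.

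**The case against.** The strongest reply is that nothing invalid is prescribed. A t-test or Mann-Whitney test is a common choice, ignoring centre errs on the conservative side, and details can go to the SAP. On validity this stands in full. On the SAP it stands in part: covariate lists and the way normality is judged are SAP matters, but the protocol has already named the tests. A SAP that follows it inherits the loss of precision, and one that departs from it has to explain why. The general sentence on additional adjusted analyses may be read to cover continuous outcomes, but it would only add to the unadjusted comparison.

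It is also fair that the correlation may be low. The baseline is taken in the short call-in period before surgery (section 4.4.1), and follow-up is 3 and 12 months after a transplant. Hence the range starts at 0.2. The centre effect on eGFR is equally uncertain, since section 10.2 has bloods analysed in local laboratories and section 4.4.4.4 in a central one.

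Four stronger readings are tempting and are not supported.

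- A reader might infer bias or false positives. The figures above show neither.
- A reader might infer that the QALY comparison is reduced to a rank test. Section 6.8 covers the economic analysis separately, aims at average costs and effects, and prescribes neither test.
- A reader might infer that Mann-Whitney breaks the promise "Outcomes will be reported with 95% confidence intervals and two-sided p-values to 3 decimal places". A Hodges-Lehmann estimate with its interval is compatible with it; only the estimator is unnamed.
- A reader might extend the point to binary outcomes. Section 6.1 already names logistic regression with adjustment for them.

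**Conclusion.** The point holds as a modest, low-cost improvement to secondary analyses. The fixed method is valid but less precise than the design allows, and its choice of summary depends on the observed data.

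For EQ-5D-5L, the gain ranges from slight (intervals 2-5% narrower at r = 0.2-0.3) to worthwhile (8-20% at r = 0.4-0.6). For the other continuous outcomes it is small: about 1-3 points of power if centre explains 2-10% of the variance. All of these rest on assumed correlations and variance shares. The primary analysis and the 131 per arm stand as they are.

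**What to change.** Replace the sentence on continuous outcomes in section 6.1 with wording to this effect:

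- Continuous outcomes are analysed by linear regression on arm and centre, with centre handled as in the primary analysis. Adjusted mean differences are reported with 95% confidence intervals.
- For EQ-5D-5L at 3 and 12 months, the baseline EQ-5D-5L score is added as a covariate.
- For skewed outcomes, robust or bootstrap intervals, or a transformation stated in advance, are used. The choice is written down per outcome before the data are seen and replaces the normality-dependent switch.
- Patients with a missing baseline EQ-5D-5L stay in the model, by mean imputation of the baseline or a missing indicator. This rule is needed because the questionnaire is optional.

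The cost is one paragraph of wording and a little more analysis work. No new data are needed, and the sample size does not change.

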## **6.2 NUMBER OF PARTICIPANTS**

### Sample size calculation

Based on the previously published paper by Treckmann et al., the 1-year graft survival for ECD kidneys preserved by SCS is being estimated at 80%. The use of HRMP is being hypothesized to improve 1-year graft survival from 80% to 92% based upon the improvement in graft survival of ECD kidneys seen in the MP Trial.

For a power of 80% with Type I error (alpha) of 5%, in a two-sided statistical model, the required sample size to detect an improvement in 1-year graft survival from 80% to 92% is 131 kidneys in each treatment arm, 262 in total.

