In experimental studies using isolated porcine kidneys, it has been shown that the outcome of potentially marginal grafts could be improved by post-hoc re-vitalization through HMP applied only at the end of the cold ischemia period (14). Here, transplanted kidneys showed improved kidney function after transplantation, when subjected to HRMP. An even higher, threefold increase in renal function could be measured, when HRMP kidneys had been perfused with oxygenated perfusion solution during machine perfusion rather than non-oxygenated perfusion solution. The benefit of a brief period of HMP just prior to renal transplantation was subsequently confirmed in a large animal auto-transplant model showing significantly improved renal function during one week after transplantation when compared to SCS alone (15). This study also demonstrated that HRMP after initial SCS preservation was equally effective at reducing early graft dysfunction after transplantation as the use of HMP during the entire preservation period. Various recent studies performed on either kidney or liver grafts give evidence for improved graft function after transplantation when oxygen is provided during machine perfusion (12, 17-18)

This study is a controlled, sufficiently powered, randomized multi-centre trial to evaluate the impact of end-ischemic reconditioning by oxygenated HMP after initial SCS on graft function of kidneys from extended criteria donors (ECD) after brain death (DBD).

While the overall study comparing HMP versus SCS as published by Moers et al. (8) had been statistically powered based on the assumption to detect a difference of at least 10% in

incidence of DGF; the subset analysis on ECD kidneys (as published by Treckmann et al. (5)) in itself had not been powered to detect one year graft survival differences. Nevertheless, the univariate analysis of this subset study on ECD kidneys revealed a significant impact of HMP on 1 year graft loss, 1-year graft function and incidence of PNF. Multivariate analysis demonstrated that HMP decreased DGF and one year graft loss.

The MP-Trial showed the potential impact of HMP in ECD kidneys. Moreover, pre-clinical studies using a large animal auto-transplant model indicate beneficial effects of short time HMP over SCS; therefore it is the goal of this study to validate these results in a clinical proof of concept study.

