The participant must personally sign and date the latest approved version of the informed consent form before any study specific procedures are performed. Written and verbal versions of the participant information sheet and informed consent form will be presented to the participants detailing the exact nature of the study, the implications and constraints of the protocol, the known side effects and any risks involved in taking part. It will be clearly stated that the participant is free to withdraw from the study at any time for any reason without prejudice to future care, and with no obligation to give the reason for withdrawal. The participant will be allowed as much time as possible to consider the information, and the opportunity to question the investigator, or other members of the clinical or research team, to decide whether to participate in the study.

A copy of the signed Patient Information Leaflet, as well as the signed and dated consent form will be given to the participant. The original signed form will be retained at the study site and a copy will be placed in the medical notes.

Subjects are free to withdraw consent at any time, irrespective of their initial consent. Subjects who withdraw consent will be replaced.

Each subject must also give permission for the sponsor's representatives to review their hospital records for the purpose of source document verification.

The subject's general practitioner/family doctor will be informed of their participation in the study.

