## **6.3 RECRUITMENT**

Each participating centre has given an estimate of expected participant numbers, fulfilling the inclusion criteria for the study.

Essen: 40 per year

Leuven: 30-45 per year

Oxford: 35-40 per year

Groningen: 20 per year

Based on these data the required number of participants will be recruited in a 2-year study period.

If recruitment is slower than anticipated then additional centres will be approached to participate in the study. Once 262 participants are recruited to the study, recruitment will stop.

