## **6.7 INCLUSION IN ANALYSIS**

The selection of participants to be included in the analyses will be detailed in the statistical analysis plan. e.g., all randomised participants, all dosed participants, all eligible participants, evaluable participants.

Only in rare cases when connection to the perfusion circuit is impossible, the kidney will be stored on ice. Data about the number of kidneys that could not be connected to perfusion circuit will be recorded; including reasons for not having connected the kidney to the perfusion circuit. These kidneys remain included in the study for Intention-to-treat analysis (i.e. in an Intention-to-treat analysis; these kidneys will be considered as HRMP kidneys despite the fact that these kidneys have actually been preserved by SCS).

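### The 262 kidneys in 6.2 are the number that must be analysed, with no allowance for loss, yet 6.3 stops at 262 recruited and the replacement rule in 4.4.1 is not reconciled with that stop

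*Protocol*

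**What the plan says.** Section 6.2 assumes 1-year graft survival of 80% with static cold storage (SCS) and 92% with machine-perfusion reconditioning (HRMP), two-sided alpha 5% and power 80%. It concludes that the number needed to detect a rise "from 80% to 92% is 131 kidneys in each treatment arm, 262 in total". It mentions no allowance for loss.

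Section 6.3 turns this into a stop rule: "Once 262 participants are recruited to the study, recruitment will stop". It lists yearly estimates for four centres and concludes: "Based on these data the required number of participants will be recruited in a 2-year study period". It also provides for approaching further centres if recruitment is slow.

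Other sections bear on how many of the 262 reach the analysis:

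- 4.3.6 excludes a kidney judged not transplantable after randomisation.
- 4.4.1 defers full consent for follow-up data until after the transplant and excludes recipients who refuse. It adds: "Subjects who withdraw consent will be replaced".
- 4.8 names withdrawal of data consent and loss to follow-up as the expected reasons for withdrawal.
- 6.7 keeps kidneys that could not be connected to the pump in the HRMP arm: "these kidneys will be considered as HRMP kidneys despite the fact that these kidneys have actually been preserved by SCS". It describes such cases as rare.

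**The concern.** A sample size with no margin meets its stated power only if every counted kidney yields a primary outcome. This protocol prescribes removals after randomisation, so 262 recruited and 262 analysed are not the same number unless the protocol makes them so.

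It does not. Section 6.2 counts kidneys and 6.3 counts recruited participants. Neither says whether a kidney excluded under 4.3.6, or a recipient excluded under 4.4.1, still uses up a place among the 262. The replacement sentence in 4.4.1 may be meant to cover part of the gap, but 6.3 does not refer to it. If the 262nd recipient is transplanted and refuses data access a week later, one section calls for a replacement and the other says recruitment has stopped.

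At stake are the accuracy of the power statement and an unambiguous end of recruitment for the sites and the trials unit.

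**Working it through.** **Inputs.** From 6.2: p1 = 0.80, p2 = 0.92, difference 0.12, mean 0.86, two-sided alpha 0.05 (z = 1.960), power 80% (z = 0.8416). From 4.1: 1:1 allocation.

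**Step 1: reproduce 131.** The two-proportion formula with pooled variance and no continuity correction is

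n = [1.960 × √(2 × 0.86 × 0.14) + 0.8416 × √(0.80 × 0.20 + 0.92 × 0.08)]² / 0.12²

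= [0.9618 + 0.4068]² / 0.0144 = 130.07, rounded up to 131 per arm, 262 in total.

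This matches exactly, so no inflation is hidden in the figure. Other common formulas give 126 (arcsine), 128 (unpooled) and 147 (continuity-corrected).

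**Step 2: power if fewer are analysed.** By the same formula,

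power(n) = Φ[(0.12 × √n − 0.9618) / 0.4833].

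The loss rates below are assumptions, because the protocol gives none. The exact column is the uncorrected chi-squared test enumerated over both binomials, at a nearby whole number of kidneys per arm. The last column is 262 / (1 − loss), rounded up.

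| Assumed loss | Analysed per arm | Power, formula | Power, exact | Randomised to keep 262 analysed |
|---|---|---|---|---|
| 0% | 131 | 80.3% | 81.2% (131) | 262 |
| 2% | 128.4 | 79.5% | 80.2% (128) | 268 |
| 5% | 124.5 | 78.2% | 79.5% (124) | 276 |
| 10% | 117.9 | 76.0% | 77.2% (118) | 292 |

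At 130 per arm the formula gives 79.98%, so one lost kidney per arm uses up its margin. Exact power does not fall smoothly: it is 79.2% at 125 and 79.5% at 124. Differences of a few tenths in that column mean little.

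**Step 3: kidneys not connected to the pump.** If 92% presumes that every HRMP kidney is perfused, and a fraction c is instead cold-stored and survives at 80%, the HRMP rate becomes 0.92 − 0.12c. At 131 per arm, c = 1% gives 0.9188 and power 79.3%; c = 2% gives 0.9176 and 78.4%. Both values of c are assumptions, and 6.2 does not say whether 92% presumes full perfusion.

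**Step 4: which losses does replacement cover?** The sentence in 4.4.1 covers consent withdrawals. Because 4.8 treats refusal of data access as withdrawal of consent, it arguably covers those recipients too. No replacement is stated for kidneys discarded under 4.3.6 or for loss to follow-up.

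**Step 5: recruitment forecast.** The low ends sum to 40 + 30 + 35 + 20 = 125 per year and the high ends to 40 + 45 + 40 + 20 = 145. Over two years that is 250 to 290, midpoint 270. The low end is 12 below 262 and the high end 28 above.

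**The case against.** The best defence has four parts.

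- **The two rules can coexist.** If a replaced subject does not count towards 262, 4.4.1 and 6.3 agree. That reading is natural, so this is an ambiguity and not a flat contradiction. It still leaves discarded kidneys and loss to follow-up without a rule, and 6.3 does not say what it counts.
- **Losses may be small.** The endpoint is whether the graft still functions at one year, and section 5 provides for data collection from referring centres. Nothing in the protocol points to heavy loss. This stands, and it limits the size of the point.
- **The exact calculation is kinder.** At about 5% loss the exact shortfall from 80% is half a point. This stands too.
- **Recruitment is hedged.** Further centres may be approached, and slow recruitment affects duration, not power, if 262 is still reached.

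Three stronger readings are tempting but unsupported. A reader might combine 5% loss with 3% non-connection (75.2%), or 10% with 5% (70.8%), and report power in the low seventies. Those figures need non-connection rates that the protocol does not give and a 92% that presumes full perfusion. A reader might also treat 125 to 145 per year as eligible patients and discount them for uptake, so that the timetable looks unreachable. But 6.3 gives expected participants who meet the inclusion criteria, and 4.3.3 lists written consent among those criteria, so a further discount may count refusals twice. Finally, a reader might conclude that the background's claim, "This study is a controlled, sufficiently powered, randomized multi-centre trial", must be withdrawn; losses of the size shown here do not justify that.

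**Conclusion.** The sample size is calculated correctly, but its power statement is not what 262 recruited will deliver. The 131 per arm is an analysed number with no slack, the protocol removes randomised kidneys and recipients, and the stop rule does not say whether those removed count.

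The effect is moderate. Assuming 5% or 10% not analysable, power is about 78% or 76% by the formula that reproduces 131, and 79.5% or 77% by exact calculation. It would be somewhat lower if 92% presumes that every HRMP kidney is perfused. It would be closer to 80% if replacement makes good the data-consent refusals. The true loss rate cannot be derived from the protocol.

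The unreconciled stop and replacement rules need no assumed rate and stand on the text alone. The two-year forecast is worded with more certainty than a range of 250 to 290 allows, but that bears on duration only. This warrants correction; it does not undermine the design.

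**What to change.** - **6.2:** State that 131 per arm is the number to be analysed. Give an explicit assumed loss rate with its basis, and restate the power for 262 randomised under it. Say whether 92% allows for kidneys that cannot be connected.
- **6.3 and 4.4.1:** Define one stopping count, for example 262 kidneys transplanted into recipients who have given data consent, and use it in both places. Say which exclusions are replaced, and how recipients whose data consent is still pending are treated when the count is reached.
- **6.3:** Give the two-year forecast as 250 to 290 and note that the low end is 12 short of 262. Keep the provision for further centres.
- **Synopsis:** Use the same definition of 262.

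The cost is an amendment to the wording and a slightly less favourable power figure. The suggested stopping count would mean randomising somewhat more than 262 kidneys, in proportion to the exclusions; loss to follow-up would then be the only loss left for the power statement to cover. If the sponsor prefers to stop at 262 randomised, no extra patients are needed and the restated power is simply accepted.
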